3.3. Intervention Dates

The intervention will be delivered to participants over a three-month period beginning in early May 2025.

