4. STUDY TIMELINE

Table 5: Study Timeline

Staff responsible/ leading	Activity	Dates
Xantura	Implementation of OneView platform and setup of predictive model	August – December 2024
Verian ([name])	Evaluation Design	August – December 2024
Verian ([name])	Scoping qualitative fieldwork with Local Authority staff and stakeholders	January – April 2025
Xantura	Data pull and predictive model run. Results shared with Verian for randomisation and then with LAs	Batch 1: April 2025 Batch 2: May 2025 Batch 3: June 2025
Local Authorities	LAs call identified households in the treatment group	Batch 1: May 2025 Batch 2: June 2025 Batch 3: July 2025
Verian ([name])	Qualitative fieldwork with project beneficiaries and residents	June – November 2025
Xantura	Secondary outcome data pulls (shared with Verian)	Batch 1: August 2025 Batch 2: September 2025 Batch 3: October 2025
Xantura	Primary outcome data pulls (shared with Verian)	Batch 1: February 2026 Batch 2: March 2026 Batch 3: April 2026
Verian ([name])	Analysis and reporting	May – October 2026
Verian ([name])	Final report publication	September 2026

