8. DATA COLLECTION

8.1. Data collection methods

All study outcomes and planned covariates come from administrative records, which will be provided by LAs on a monthly basis and collated within the OneView platform. Additionally, call handlers will use OneView to record their attempts and success at making the treatment calls to support the compliance analysis and IPE. Xantura will have responsibility for managing data collection, ensuring data quality, and minimising missing information. They will provide household-level risk scores for the randomisation and then will deliver outcome data at the 2-month and 9-month follow-ups.

Timelines

For each batch, the trial will begin with randomisation, followed by a 1-month intervention period in which LAs deliver the calls to treatment households, with the two follow-up data collection points occurring 2 and 9 months after the end of the intervention period.

Table 6: Data collection procedures and assessment timeline

Assessment point	Type of data	Data collection approach
Pre-trial Batch 1: April 2025 Batch 2: May 2025 Batch 3: June 2025	Baseline characteristics of the sample All administrative data from LAs Risk scores from Xantura's predictive model (for randomisation)	Data collected from LA records by Xantura via OneView
1-month Intervention period Batch 1: May 2025 Batch 2: June 2025 Batch 3: July 2025	Outcomes related to the proactive call made to individuals in at risk households.	Data collected from LA call handlers by Xantura via OneView
2-month follow-up Batch 1: July 2025 Batch 2: August 2025 Batch 3: September 2025	Secondary outcome data	Data collected from LA records by Xantura via OneView

9-month follow-up Batch 1: February 2026 Batch 2: March 2026 Batch 3: April 2026	Primary outcome data Secondary outcome data	Data collected from LA records by Xantura via OneView
---	--	---

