Time Horizon

We will follow CHI's guidance on the evaluation time horizon to ensure consistency with other interventions within the wider Test and Learn programme. In line with that guidance, this economic evaluation will consider all costs and cost savings accruing throughout the time period of the impact evaluation (January 2024 – January 2025).

We will provide estimates of the cost saving unit values (see Table 10 for further details) on a per household / per person per year basis and apply these in line with the evaluation time horizon. Where relevant (and supported by appropriate evidence), we may consider either a shorter or a longer time horizon – e.g. in case of cost savings sustained in the long term. Where this is the case, we will consider a range of plausible time horizons as part of the sensitivity analysis.

In case we find that the intervention costs exceed the cost savings within the core evaluation time horizon, we will include a break-even analysis over time. This will consider a scenario where the intervention is continued on an ongoing basis, applying the intervention to further cohorts of at-risk households over subsequent years. As part of this break-even analysis, we will carry out an assessment out of the level of intervention impacts (in terms of fewer households being owed a relief duty because they have become homeless), intervention costs, and cost savings that would apply in subsequent years of the intervention.

Costs

Costs of delivering the intervention include all of the following: direct costs of the Xantura OneView platform license fee, direct LA costs of staff time spent on setting up the predictive model to identify individuals at risk of homelessness using OneView data platform, direct LA costs of ongoing maintenance and monitoring of the platform, direct LA costs of the preparation and delivery of the intervention phone calls, and indirect LA costs of providing proactive support to members of at-risk households assigned to the RCT treatment group.

Costs of delivering the counterfactual include only the indirect LA costs of providing business as usual support to members of at-risk households assigned to the RCT

control group. If we see significant variation between LAs we will report the range of costs with, where available, information about the factors that seem to drive greater BAU costs.

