Access to each folder containing personal data will be limited to those who have a legitimate need to access that data. Participant data will be linked using a pseudonymous ID number. Except where necessary for the collection of IPE data, Verian researchers will not have access to participant contact details. The research will end in January 2026 and personal data will be retained by Verian until 31 January 2027. Simetrica-Jacobs will transfer cost evaluation data to Verian and then delete it, no later than 30 September 2026. Participants may also ask their LA and/or MHCLG to delete their personal data from the study at any time.

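### The economic evaluation's core time horizon is dated January 2024 to January 2025, which cannot be the impact evaluation period it is said to be

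*Protocol*

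**What the plan says.** Protocol section 12.2, under Time Horizon, fixes the core period: "this economic evaluation will consider all costs and cost savings accruing throughout the time period of the impact evaluation (January 2024 – January 2025". The horizon is thus defined in words, as the impact evaluation period, and then given dates.

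Other sections date that period differently:

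- Section 3.3: "The intervention will be delivered to participants over a three-month period beginning in early May 2025".
- Section 4, Table 5, data pull, model run and sharing for randomisation: "Batch 1: April 2025 Batch 2: May 2025 Batch 3: June 2025".
- Section 4, Table 5, calls to the treatment group: "Batch 1: May 2025 Batch 2: June 2025 Batch 3: July 2025".
- Section 4, Table 5, primary outcome pulls: "Batch 1: February 2026 Batch 2: March 2026 Batch 3: April 2026".
- Section 8.1 gives the rule behind the last of these: "with the two follow-up data collection points occurring 2 and 9 months after the end of the intervention period".

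Table 5 also has a row for "Implementation of OneView platform and setup of predictive model", dated August to December 2024.

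The horizon is used in three places. Section 12.2 applies annual unit savings in line with it and makes a break-even analysis conditional on costs exceeding savings within it. Section 12.4 lists it among the assumptions of the value-for-money spreadsheet.

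A further date bears on this. Section 16.3 says: "The research will end in January 2026 and personal data will be retained by Verian until 31 January 2027".

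**The concern.** A time horizon decides which costs and savings count. Here the dates and the definition cannot both hold. If the dates are followed, the period includes platform set-up but stops before any household is randomised, called or followed up. If the definition is followed, the dates are wrong, and the reader must work out the right ones.

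That is not a trivial choice, because the plausible corrections differ on whether set-up costs fall inside the horizon. Section 12.2 wants set-up counted, and section 12.1 wants upfront costs distinguished from ongoing ones. The section also ties the horizon to CHI guidance so that results can be compared across the programme, which needs an unambiguous period. If the dates stay as they are, someone will have to choose the horizon once outcomes are known.

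**Working it through.** The check is calendar arithmetic. Number the months so that January 2024 = 1. Then August 2024 = 8, December 2024 = 12, January 2025 = 13, April 2025 = 16, May 2025 = 17, July 2025 = 19, January 2026 = 25, February 2026 = 26 and April 2026 = 28.

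**Step 1: is the schedule consistent with itself?** Call month plus 9 gives 17 + 9 = 26, 18 + 9 = 27 and 19 + 9 = 28, that is February, March and April 2026. This matches the primary outcome pulls in Tables 5 and 6, so the dates in section 12.2 are the outlier.

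**Step 2: what does the stated window (months 1–13) contain?** Overlap = max(0, earlier end − later start + 1).

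| Activity | Months | Overlap with 1–13 |
|---|---|---|
| Platform and model set-up | 8–12 | 12 − 8 + 1 = 5 of 5 |
| Data pull and randomisation | 16–18 | 13 − 16 + 1 = −2, so 0 of 3 |
| Calls | 17–19 | 13 − 17 + 1 = −3, so 0 of 3 |
| Primary outcome pulls | 26–28 | 13 − 26 + 1 = −12, so 0 of 3 |

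The window's last month falls 16 − 13 = 3 months before the first data pull, 17 − 13 = 4 before the first call month and 26 − 13 = 13 before the first primary outcome pull. Section 3.1 allows follow-up calls for up to 6 months. If these run from the last call month they could reach month 19 + 6 = 25, and none of months 17–25 lies in the window either.

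**Step 3: which dates would repair it?**

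| Candidate horizon | Length | Set-up | Randomisation | Calls | 9-month pulls |
|---|---|---|---|---|---|
| As stated, 1–13 | 13 | 5 of 5 | 0 of 3 | 0 of 3 | 0 of 3 |
| One year later, 13–25 | 13 | 0 of 5 | 3 of 3 | 3 of 3 | 0 of 3 |
| April 2025 to April 2026, 16–28 | 28 − 16 + 1 = 13 | 0 of 5 | 3 of 3 | 3 of 3 | 3 of 3 |
| August 2024 to April 2026, 8–28 | 28 − 8 + 1 = 21 | 5 of 5 | 3 of 3 | 3 of 3 | 3 of 3 |

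A one-year slip therefore does not explain the text. The third row is the impact evaluation period on the protocol's own schedule. It needs a separate statement that the earlier set-up costs are included.

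**Step 4: the research end date.** January 2026 is month 25. The primary outcome pulls are months 26–28, and Table 5 puts analysis and reporting in May to October 2026. The end date in section 16.3 precedes all of these.

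**The case against.** The best defence is that the words govern and the dates are a leftover. The sentence names the impact evaluation period. The same section lists call delivery and proactive support among the costs to count, and section 12.3 takes the number of beneficiary households from the impact evaluation. An analyst who followed the dates would have to ignore those instructions. This stands: the dates look like an error, not a design.

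It also limits the consequences. A reader might infer that net value is bound to come out negative and that the break-even analysis is bound to run. The protocol does not support either. Savings are not summed from spending dated within the window. They are built from annual unit values multiplied by the estimated number of beneficiary households, with the horizon entering as an assumption. On that method the length matters more than the calendar position, and the stated window and April 2025 to April 2026 are both 13 calendar months. If the window truly held no beneficiaries, results per beneficiary household would be undefined, not negative.

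Nor should the statement that the window contains set-up be stretched to all upfront costs. Call-handler training and the licence fee carry no dates, and the April–June 2025 model runs fall outside the window.

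The defence does not remove the contradiction. The option of a shorter or longer horizon is discretionary and handled in sensitivity analysis, and the break-even analysis concerns later cohorts. Neither changes the core dates.

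The end date in section 16.3 is a separate matter. It does not define the economic horizon, and data retention to 31 January 2027 runs past the planned analysis.

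**Conclusion.** The bracketed dates are wrong as written. They contain 5 of 5 set-up months, 0 of 3 call months and 0 of 3 primary outcome pulls, and they contradict both the definition they illustrate and the section's own cost list. The conclusion rests only on the protocol's dates, read at calendar-month resolution. No monetary effect can be computed from the document, and none is claimed.

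This is a moderate point. Randomisation, outcomes and the impact models are untouched, and the intended period can be inferred. It still deserves correction, because the horizon is an operating input to the economic result and the obvious one-year shift gives another wrong window. The January 2026 end date is a smaller inconsistency of the same kind, with no shown effect on any analysis.

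**What to change.** Before outcome data are analysed:

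1. In section 12.2, replace the dates with the actual impact evaluation period: April 2025 (batch 1 randomisation) to April 2026 (batch 3 nine-month follow-up).
2. State there that set-up costs from August 2024 are included as upfront costs, using the split that section 12.1 already makes.
3. Use the corrected horizon in the section 12.4 assumptions, in the condition for the break-even analysis and in the reporting period of the cost form. Section 12.3 still shows distribution of that form as to be confirmed, so its period should be checked.
4. In section 16.3, reconcile the January 2026 end of research with the February–April 2026 outcome pulls and the May–October 2026 analysis.

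The way annual savings accrue need not change. Accrual over each household's own follow-up would be a new method, and it could not be checked against the CHI guidance that the section cites.

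The cost is a few lines of text and a check of the cost form. No new outcome data are needed.

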 - *Indirect costs* to the participating LAs – that is, costs in relation to providing support services to at-risk individuals from households identified by the model, beyond the initial intervention phone call delivered by the LA. This will include

the costs of any follow-up phone calls made by the call handler and costs of the support service(s) taken up as a result of the intervention signposting.

- Identify the cost savings to the public sector resulting from the intervention. This will include cost savings that arise either directly due to members of beneficiary households avoiding homelessness or indirectly – where avoided homelessness leads to another ‘downstream outcome’, such as better health, which then creates cost savings.
- Review and collate evidence linking the number of beneficiary households to the probability of accruing the costs/cost savings identified above.
 - *Beneficiary households* are the households at risk of homelessness (per the predictive model), whose members avoid being owed a relief duty because they have become homeless. This is intended to align with the definition of *intervention impact* – the number of beneficiary households – to be measured through the impact evaluation.⁴
- Assess the overall Value for Money delivered by the intervention.

Research Questions

Our overarching question is whether the intervention provided value for money. In order to answer it, we will investigate the following four research questions:

1. How much was the overall cost to the public sector of delivering the intervention? This will consider costs to the participating LAs over and above business as usual, including both direct and indirect delivery costs, as well as the license fee for the Xantura OneView platform provided to the LAs to enable the intervention.
2. How much money is saved by the public sector as a result of fewer households being owed a relief duty because they have become homeless?

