12.2. Research Design and Methods

Overall Approach

Given the economic evaluation's focus on the public sector costs and cost savings associated with the intervention, and the wider aim of comparing the relative performance of different Test and Learn interventions, the intervention's Value for Money will be assessed using **Cost Effectiveness Analysis** (CEA). This will involve calculating the intervention's cost effectiveness ratio (delivery cost of intervention vs business as usual, per beneficiary household) - and comparing it against the following reference points:

- other initiatives within the wider Test & Learn and Systems-Wide Evaluation Programme (subject to availability of the relevant evaluation results)
- a breakeven benchmark given by the cost savings for the public sector per one beneficiary household.

To be considered good value for money, the intervention would be expected to have a cost efficiency ratio below the breakeven benchmark. This would indicate that the intervention has:

1. created a positive impact by reducing the number of at-risk households whose members are owed a relief duty because they have become homeless, compared to the counterfactual, and
2. reduced public spending by more than it cost to deliver, compared to the counterfactual.

Relevant Alternatives/ Counterfactuals

The intervention costs, including cost savings, will be assessed relative to a counterfactual BAU scenario.

The definition of this counterfactual scenario will be aligned with the impact evaluation approach, to ensure that both the beneficiaries and the intervention costs are assessed in a consistent way. The counterfactual will be represented by the control group of the RCT, who will receive standard homelessness prevention and support services offered by the LAs participating in the project to individuals at risk

of homelessness. Unlike the treatment condition, participants receiving BAU will not receive a phone call from the LA referring them to relevant support services.

Evaluation Perspective and relevant stakeholders

The proposed approach to the economic evaluation considers the costs and cost savings associated with the intervention. Costs and cost savings will be assessed focusing on the perspective of all major public sector stakeholders (LAs, Central Government and the NHS), acknowledging their wider impacts on the society, in particular on the quality of life of the individuals affected; as well as from the LA perspective.

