These costs are expected to accrue directly to the LAs participating in the project. However, given the project's RCT implementation structure, each LA will be providing services simultaneously to the intervention and control groups – whilst funding them through a range of sources, including:

- Unitary/Lower-tier LA own budget
- Upper-tier LA funding
- MHCLG Rough Sleeping Initiative grants,⁵ a multi-year programme providing local councils with long-term funding to support those sleeping rough or at risk of rough sleeping
- Other central government funding.

Therefore, it would not be practical to differentiate between the intervention and BAU delivery costs according to their funding source. Instead, we recommend that these costs are assessed based on spending data collected from the participating LAs through the dedicated Cost Data Submission Tool.

The table below provides further detail on the spending categories to be considered as part of the Cost Data Submission Tool.

Table 9: Economic Evaluation costs

Cost	Supplementary Data Source	Notes
Intervention only		
Direct costs OneView platform license fee (market value) LA resources (salaries, time, overheads, fees) spent on: Setup, monitoring and maintenance of OneView data Call handler training Casework (intervention phone calls providing proactive support) Administration of intervention	Cost Data Submission Tool*	
Intervention and counterfactual		

⁵ [Rough Sleeping Initiative: 2022 to 2025 funding allocations](#)

Indirect costs LA resources (salaries, time, overheads, fees) spent on: Running cost of existing support services	Cost Data Submission Tool* Can be triangulated against relevant Simetrica-Jacobs exchequer values ⁶ estimated for the HACT UKSVB ⁷	To be apportioned according to service uptake in intervention and control groups ⁸
--	---	---

** LAs will be provided with a comprehensive **cost** form to populate. A copy of the Cost Data Submission Tool will be provided separately.*

Benefits (and averted costs)

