Council tax arrears	Xantura predictive model data – based on LA Council Tax arrears records, split by intervention and control group	Reduced Council Tax debt
Council housing rent arrears	Xantura predictive model data – based on LA records on Council housing rent arrears, split by intervention and control group	Reduced Council housing arrears
Emergency relief services annual budget	https://www.mannasociety.org.uk/ within Crisis report (2016), p.26 ¹⁰	Reduced need for emergency relief services ¹¹
Average weekly (social and affordable) rent (2022/23)	Live tables on rents, lettings and tenancies 2022/23, MHCLG	Increased financial support to gain/maintain secure housing in the social rented sector
Government expenditure on housing element of Universal Credit (GB) (2022/2023)	Benefit expenditure by country and region, 1996/97 to 2022/23, DWP	Increased financial support to gain/maintain secure housing in the private rented sector
Cost of unemployment benefits	Based on Simetrica-Jacobs' exchequer values estimated for the HACT UKSVB	Avoided loss of full-time employment

¹⁰ The report uses the annual cost data, which is published by a day centre in London, seeing between 150-180 single homeless people per day and with an annual budget amount reported.

¹¹ This may not constitute a cost to the public sector if the services are provided e.g. by a housing association.

Cost of NHS services for those in poor overall health	Based on Simetrica-Jacobs' exchequer values estimated for the HACT UKSVB	Avoided deterioration in overall health
---	--	---

Note: The outcome-level estimates considered above will be triangulated against other existing estimates of the overall costs of a homelessness application, e.g. from the GMCA Unit Cost Database or the upcoming research from LSE/MHCLG.

Sensitivity Analyses

Sensitivity analysis will aim to reflect the level of estimation uncertainty around key components of the economic evaluation calculations, including (where relevant):

- Number of beneficiary households – e.g. using confidence intervals around the central impact estimates from the impact evaluation
- Cost of delivering the intervention – e.g. using a high-low range of additional intervention implementation costs to the LAs, depending on the variation in responses to the Cost Data Submission Tool (see more details in section 12.3)

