Annex B: Call Guidance for Local Authorities

2. Understand their perspective and needs

- a. Using the information provided on Oneview about the individual to start a conversation about potential avenues of support (don't refer specifically to

interactions with the local authority but use the information you have to inform the direction of the conversation/the offers of support)

- i. **If you are satisfied you have completed your needs assessment of the household please enter this in OneView as assessment completed**

- 3. Signpost or complete warm handovers¹⁴ (a warm handover is where you arrange a follow up appointment or directly transfer a person to the team that can offer advice and support) to relevant services - within the buckets
 - a. Financial health
 - i. Debt Advice

Local Services: **ADD IN HERE**
 National Services: Citizens' Advice [contact] (debt helpline) or [Debt Advice - CAB](#), Step Change [contact] [Step Change](#)
 - ii. Welfare Benefits Advice

Local Services: **ADD IN HERE**
 National Services: [Entitled To](#)
 - b. Emotional wellbeing

Local Services: **ADD IN HERE**
 National Service that links to local provision: Call NHS 111 Press 2
[National services: Shout \(text service\) Samaritans Call [name]](#)
 - c. Physical health

Local Services: **ADD IN HERE**
 - d. Housing support

Local Services: **ADD IN HERE**

- 4. Close -
 - a. Ask the person you are talking to if they understand what you have been talking about and if they need anything explaining. Ask them if there is anything that hasn't been covered where they want support.
 - b. Explain what will happen next
 - i. "I have given you the contact details for X and you have said you will contact them" or
 - ii. I have made a referral for you to Y, they will be in touch with you shortly."¹⁵

¹⁴ This will vary from call to call and by local areas. Some people will want to make their own arrangements and in some areas there may not be capacity to complete warm handovers. The outcome is recorded in OneView and this will be taken into account through the evaluation. Warm handovers generally result in improved outcomes for individuals.

¹⁵ London Borough of Barking and Dagenham also plan to use follow up texts 'Dear XYZ, Following your consultation, please see below your personalised care plan. Goals: X Agreed Actions: X Next Steps: X Next Contact Date: X Best wishes, X'

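### The economic evaluation takes a whole-public-sector perspective, but its cost list holds only local-authority costs and the platform licence fee, so call-prompted NHS use and non-housing benefit awards have no line

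*Protocol*

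**What the plan says.** Protocol section 12.1 makes net value to the public sector the primary aim and the LA view the secondary one. Section 12.2 (evaluation perspective) applies the wide view to both sides of the account: "Costs and cost savings will be assessed focusing on the perspective of all major public sector stakeholders (LAs, Central Government and the NHS"), with an LA view alongside.

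The cost side is drawn more tightly. Research question 1 in section 12.1 reads "How much was the overall cost to the public sector of delivering the intervention? This will consider costs to the participating LAs" and then brings in the licence fee. The Costs paragraph of section 12.2 lists the licence fee, LA staff time for set-up, LA maintenance and monitoring, LA preparation and delivery of the calls, and finally "indirect LA costs of providing proactive support to members of at-risk households assigned to the RCT treatment group". The text after that list says "These costs are expected to accrue directly to the LAs participating in the project". Table 9 has the licence fee at market value and LA resources, and nothing else.

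The savings side is wider. Table 10 includes "Cost of NHS services for those in poor overall health" and the cost of unemployment benefits. It also lists housing support in the social and private rented sectors. The text before Table 10 treats Universal Credit or Housing Benefit for a household that keeps its home as a central-government cost, and says offsetting entries between public bodies will be reflected. All these items are applied to beneficiary households or to their members.

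Annex B gives call handlers a menu of services, including welfare benefits advice, physical health, and, under emotional wellbeing, "National Service that links to local provision: Call NHS 111 Press 2".

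**The concern.** Value for money is judged by comparing delivery cost per beneficiary household with public-sector savings per beneficiary household. A ratio below that benchmark is to be read as showing that public spending fell by more than the intervention cost. That reading needs every public cost the intervention causes to appear somewhere in the comparison.

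Some foreseeable ones do not. A call meant to raise engagement with services can lead to NHS contacts and to new benefit awards outside the housing element. These can arise in any treated household that follows up a referral, whether or not it would otherwise have been owed a relief duty. They are not LA costs, so the cost list misses them. Most would arise outside beneficiary households, so Table 10 misses them too. An intervention that moved part of its cost to the NHS or to central government could then pass a test described as public-sector-wide.

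**Working it through.** The protocol states no cost, saving or net-value figure, so there is no economic result to reproduce. The check is a comparison of who pays, followed by a scaling calculation.

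**Step 1: payers on each side.**
- Perspective (12.2): LAs, central government and NHS, for costs and savings.
- Costs (12.1 research question 1, 12.2 Costs, Table 9): LA direct and indirect costs, plus the licence fee. Section 2.1 says the ministry funds the LAs' use of the model, so one cost financed outside the LAs is counted.
- Savings (Table 10): LA, NHS and unemployment-benefit items, with housing support as an offset.
- Not on either side: NHS contacts and non-housing benefit awards prompted by the call.

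**Step 2: could another line absorb them?**
- The objectives in 12.1 mention services taken up because of the signposting, but under indirect costs to participating LAs.
- The housing-support offset applies to beneficiary households only.
- The sensitivity analyses name four components: number of beneficiary households, delivery cost (from the variation in LA cost returns), unit values of savings, and probabilities of savings. None adds a cost category.
- The 10-15% optimism-bias adjustment scales costs already counted.
- A footnote to Table 9 accepts that uptake of third-party services is harder to obtain, but gives no fallback.

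**Step 3: what the omission does to the test.** Let D be the net delivery cost per treated household as the plan counts it, S the public saving per beneficiary household, d the risk reduction, and c the net uncounted public cost per treated household (treatment minus control).
- Plan's test: pass if D/d < S.
- Complete test: pass if (D + c)/d < S.
- The two disagree when D/d is below S by less than c/d. If c is negative, the plan's test is too strict instead.

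**Step 4: scale of c/d.** The only effect range in the protocol is the minimum detectable effect of 2-7 percentage points (9.1 and Table 7). It is used here for scale, not as a forecast. With 800 per arm (Scenario C: 2,000 × 0.8 = 1,600), two-sided 0.05 and power 0.8, the usual two-proportion formula gives 1.97 points at a 3% base rate, 6.98 at 50% and 2.48 at 98%, which agrees with the stated range.
- Treated households per beneficiary household = 1/d: 1/0.07 = 14.3, and 1/0.02 = 50.
- c = £10 (assumed): 10/0.07 = £143, and 10/0.02 = £500 per beneficiary household.
- c = £100 (assumed): 100/0.07 = £1,429, and 100/0.02 = £5,000.
- By take-up, c = u × s, where u is the incremental take-up share and s the unit cost. With u = 5% and s = £1,000 (both assumed), c = £50. That gives £714 at 7 points, £1,000 at 5 points and £2,500 at 2 points.

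The multiplier follows from the plan's own denominator. The values of c, u and s do not come from the protocol.

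**The case against.** The strongest reply is that the list is a delivery-cost list by definition. Section 12.2 defines the ratio's numerator as delivery cost against business as usual, and effects on other public bodies are dealt with through Table 10. This stands as a description of the ratio. It does not rescue the conclusion that public spending fell, because Table 10 reaches only beneficiary households.

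Several stronger readings are tempting, and the protocol does not support them.
- *That only LA costs are counted.* The licence fee is counted, use of the model is centrally funded, and part of the LA spending is itself financed by central grants.
- *That benefit take-up is ignored.* Housing-related support is named as a central-government cost and has data sources in Table 10. The gap is non-housing awards, and take-up among treated households that are not beneficiary households.
- *That every reached household is sent to the NHS and to benefits advice.* Annex B is a menu chosen by need, and section 11.2 provides for calls that end with no referral.
- *That net public value is overstated.* Health or employment gains among treated households outside the beneficiary group are also uncounted, and prompted NHS contact may lower later NHS spending. Omissions run both ways.

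Two possible remedies would also be wrong. Costing treatment-arm referrals as if they were all additional is not incremental, since control households can use the same services and have no referral record. Making the LA-only ratio the headline would reverse the stated primary and secondary aims.

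**Conclusion.** The cost list does not match the stated perspective. LA costs plus the licence fee are set against savings that extend to the NHS and unemployment benefits, and NHS contacts and non-housing benefit awards prompted by the call have no line. The public-sector breakeven test may therefore be too favourable.

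The multiplier of 14 to 50 treated households per beneficiary household shows that a small average cost could matter. It rests on the detectable-effect range standing in for the true effect. Whether such a cost exists, how large it is and its net sign cannot be settled from the protocol. The point bears on the value-for-money conclusion and leaves the trial's primary effect estimate untouched.

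**What to change.** Keep the public-sector ratio as primary. Align research question 1 and the Costs paragraph with the stated perspective, and add to Table 9 and to the sensitivity analyses one line for incremental (treatment minus control) NHS and non-housing benefit costs of signposted services.

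- Where OneView holds uptake by arm, use the difference between arms.
- Otherwise, multiply the treatment-arm referrals, already recorded by service (section 11.2), by a unit cost over a stated range of incremental take-up, from zero to all referrals taken up. Label the top an upper bound, because control uptake is not observed.
- State in 12.2 that the report will conclude that public spending fell only if breakeven holds across that range. If it does not, report the public-sector ratio as incomplete on the cost side, next to the LA-perspective result already planned.

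This costs a few unit values and one more scenario, with no new data collection. The downside is a possibly less favourable ratio.
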